Appendix 1.

On the next page are four letter formats. One factor is the presence of an authority figure giving staff access to the vaccinations. The authority figure is [name], the Chief Executive and also a medical doctor. The other factor is the presence of descriptive norms describing the proportions of staff that have been vaccinated in peer hospitals.

Within the examples the highlighted areas indicate where these two factors are active.

GREEN = authority factor.

YELLOW = norms factor.

Short Title: An improvement project around staffs' influenza vaccine uptake

Emailed Letters.

Letter one

Dear colleague,

You are invited to take up your free flu jab this season to reduce your risk, and your patients' risk, of getting the flu.

Find out how to get your jab at the Trust, please visit the [] part of the Intranet or ask your line manager.

We appreciate your support in keeping colleagues and patients safe,

Occupational; Health Department

Letter two

Dear name,

I am inviting you to take up your free flu jab this season to reduce your risk, and your patients' risk, of getting the flu.

Last winter, the national expectation was for at least 70% of frontline staff to be vaccinated against seasonal flu. That was achieved at QEHB, with **71.6%**, and at Heartlands, Good Hope and Solihull with **73.5%**. This year, the national expectation is for 75% of frontline staff to be vaccinated.

However, we want UHB to be amongst the very best performers of similar hospitals, so that we maximise protection for our staff and patients. We know it is entirely achievable, with your support, for us to reach or surpass the levels of some of the best performers from last year:

Royal Liverpool & Broadgreen	86.9% of frontline staff vaccinated
Cambridge University Hospitals	84.3%
Birmingham Children's Hospital	82.1%
Leeds Teaching Hospitals	80.8%
Guy's and St Thomas's	79.9%

In the United States 92% of hospital staff receive flu vaccination.

Find out how to get your jab at the Trust, please visit the [] part of the Intranet or ask your line manager.

I appreciate your support in keeping colleagues and patients safe,

Kind regards

Occupational Health Department

Letter three

Dear colleague,

You are invited to take up your free flu jab this season to reduce your risk, and your patients' risk, of getting the flu.

Last winter, the national expectation was for at least 70% of frontline staff to be vaccinated against seasonal flu. That was achieved at QEHB, with **71.6%**, and at Heartlands, Good Hope and Solihull with **73.5%**. This year, the national expectation is for 75% of frontline staff to be vaccinated.

However, we want UHB to be amongst the very best performers of similar hospitals, so that we maximise protection for our staff and patients. We know it is entirely achievable, with your support, for us to reach or surpass the levels of some of the best performers from last year:

Royal Liverpool & Broadgreen	86.9% of frontline staff vaccinated
Cambridge University Hospitals	84.3%
Birmingham Children's Hospital	82.1%
Leeds Teaching Hospitals	80.8%
Guy's and St Thomas's	79.9%

In the United States 92% of hospital staff receive flu vaccination.

Find out how to get your job at the Trust, please visit the [] part of the Intranet or ask your line manager.

We appreciate your support in keeping colleagues and patients safe,

Occupational; Health Department

Letter four

Dear name,

I am inviting you to take up your free flu jab this season to reduce your risk, and your patients' risk, of getting the flu.

Last winter, the national expectation was for at least 70% of frontline staff to be vaccinated against seasonal flu. That was achieved at QEHB, with **71.6%**, and at Heartlands, Good Hope and Solihull with **73.5%**. This year, the national expectation is for 75% of frontline staff to be vaccinated.

However, we want UHB to be amongst the very best performers of similar hospitals, so that we maximise protection for our staff and patients. We know it is entirely achievable, with

Version 2.0

7 September 2018.

14 of 15

Page

Short Title: An improvement project around staffs' influenza vaccine uptake

your support, for us to reach or surpass the levels of some of the best performers from last year:

Royal Liverpool & Broadgreen **86.9%** of frontline staff vaccinated

Cambridge University Hospitals **84.3%**

Birmingham Children's Hospital **82.1%**

Leeds Teaching Hospitals **80.8%**

Guy's and St Thomas's **79.9%**

In the United States 92% of hospital staff receive flu vaccination.

Find out how to get your job at the Trust, please visit the [] part of the Intranet or ask your line manager.

I appreciate your support in keeping colleagues and patients safe,

Kind regards

[name]

Chief Executive

References.

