Primary: Will the content of different wording on the letters requesting NHS staff to receive the seasonal influenza vaccination affect the rate at which those staff are vaccinated?

Secondary: Will the effect sizes vary across different demographics?

Data/Outcomes.

- Staff IDs- this is needed to randomize and send letters-Will be deleted after data collection ceases
- Staff Name-this is needed to address letters, e.g., “Dear [name]” -Will be deleted after data collection ceases
- Group Number (e.g., 0=letter version one, 1=letter version two, 2=)
- Date of Vaccination at Trust (DD-MM-YYYY, or blank if the vaccination was never received),
- Indicating Refusal to take up the vaccination (0=No, 1=Yes),
- Indicating Vaccinating at non-Trust Location, e.g., general practice (0=No, 1=Yes)

There are no secondary outcome measures, but information related to the participants’ worksite, job role and gender will be used as predictors in the secondary analyses.

- Worksite (0=Queen Elizabeth, 1=Heartlands, 2=Solihull, 3=Good Hope),
- Job role (1=Doctor, 2=Nurse, 3=Other-frontline), 4=Other-non-frontline),
- Gender (0=Female, 1=Male, 2=Not indicated).

Data retrieval will be facilitated by UHB’s Clinical Business Development Lead from UHB's MyFluJab database, and from Occupational Health data systems.

Analyses.

The primary analysis will compare the proportions of staff that take up the vaccination in each group, where each group receives a different letter. The rates of vaccination will be analyzed with a binary logistic regression model including an interaction term and the two main effects. While all forms of wording will encourage uptake, we hypothesise that some will work better than others.

The secondary analysis will look for differences in the letter wording effectiveness related to sub-group demographics, i.e., worksite, job roles, and gender.

Analyses will be conducted by a UHB statistician according to UHB’s secure protocols.

Short Title: An improvement project around staffs' influenza vaccine uptake

Summary of main issues.

No significant ethical, legal, or management issues arise from this study.

The largest risk of this study is the opportunity for NHS staff data to be leaked. To minimize this risk, no individual-level data will be transferred across organizations. Rather all data will be retrieved and analyzed by authorized UHB staff.

Scientific Justification.

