This research is worth doing because current vaccination rates among NHS staff remain lower than desired. The variation among NHS trusts' vaccination rates (from less than 40% to more than 80%)⁶ suggests that some trusts' may doing something better. Unfortunately, reviews of past data do not easily indicate malleable factors as to why the rates differ. The current study will examine one malleable factor that may affect uptake rates, i.e., the content of letters asking staff to vaccinate.

Design and methodology.

Null Hypothesis: All the letters will similarly influence the rate at which staff take up the vaccination.

Alt Hypothesis: The letters will differently influence the rate at which staff take up the vaccination.

The RCT method was selected, because it is the most robust method through which to make causal inferences. The RCT method is feasible, because UHB already monitors whether each staff member receives the vaccination.

There will be no 'no-treatment' control group. All letters will non-coercively invite NHS staff to take up the vaccination, though we expect some reminders to work better than others.

Letter wordings are given Appendix A. One factor will emphasize an authority figure inviting staff to vaccinate. The other factor will emphasize a competitive social norm describing peer hospital performance. Letters will be sent both by e-mail and through the internal post.

UHB's Clinical Business Development Lead will send UHB's statistician a data file in mid-September containing information about staff who should be invited to have a vaccination:

- (1) IDs-needed to randomize at an individual level
- (2) Staff Name-needed to address reminders, e.g., "Dear [name]"
- (3) Worksites-needed to stratify randomization, and
- (4) Job Roles-needed to stratify randomization.

We expect this file to include up to 18,000 NHS staff members, and this number is more than sufficient for our primary comparison. UHB's statistician will randomize these staff to receive one of the letters and then will help UHB's communications team to disseminate the letters according to the randomized schedule.

In January UHB's Clinical Business Development Lead will send UHB's statistician a data file describing whether those staff randomized to receive a letter went on to get vaccinated by the 4th of January. The data will contain information describing each staff member's:

- (1) ID,
- (2) Worksite,
- (3) Job Role,
- (4) Gender,
- (5) Group,

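### In the intended two-by-two design, being greeted by name is fully aliased with the authority factor, so an effect cannot be credited to authority alone

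*Combined protocol and SAP*

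**What the plan says.** Protocol Appendix 1 describes the factor in terms of who is inviting: "One factor is the presence of an authority figure giving staff access to the vaccinations". The protocol's Summary of study and Design and methodology sections describe it in the same way. None of these places mentions how the recipient is addressed.

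The letters in Appendix 1 differ in more than that. Letters one and three open "Dear colleague" and continue "You are invited to take up your free flu jab this season". Letters two and four open with a placeholder for the recipient's name, continue "I am inviting you to take up your free flu jab this season", and close "I appreciate your support in keeping colleagues and patients safe" followed by an extra courtesy line (Kind regards).

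The protocol body does not tie names to particular groups. Data/Outcomes has "Staff Name-this is needed to address letters", and Design and methodology has "Staff Name-needed to address reminders".

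In the SAP, Objective 1 (section 3) assesses the effects of Social Norms, Authority and their interaction. The primary model (section 5) has one 0/1 Authority term, one 0/1 Social Norms term and their product, with no term for personal address. SAP section 2 gives 1,885 staff in each of the four letter groups.

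**The concern.** Greeting someone by name is a different ingredient from having the Chief Executive do the inviting. If the name appears in exactly the authority letters, a higher uptake in those groups could come from the name, from the sender, or from both, yet the SAP would report it as an effect of Authority.

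The practical stake is which ingredient the Trust should keep. Any department can use names, but only the Chief Executive can supply that authority. Repairing the other faults in letter two (its norms text and its departmental sign-off) would leave the greetings as they are, so the point needs its own correction.

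**Working it through.** **The plan's own figure.** The protocol's Participants section gives at least 750 per group for an interaction with uptake of 40%, 40%, 40% and 50%, at alpha 0.05 and 80% power (its beta of 0.8 is read as power). With n = (1.96 + 0.84)² × V / effect², two-sided:

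- Risk-difference scale: V = 3 × 0.24 + 0.25 = 0.97, effect 0.10, n = 762.
- Log-odds scale: V = 3/0.24 + 1/0.25 = 16.5, effect ln 1.5, n = 788. Power at 750 is 0.78.

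The stated 750 is close to both. With 1,885 per group, power for that interaction is about 0.99. Sample size is not the difficulty.

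**The letters as printed.**

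| Letter | Greeting | Voice | Norms text | Signed by |
|---|---|---|---|---|
| One | colleague | impersonal, then plural | no | Occupational Health |
| Two | name | first person singular | yes | Occupational Health |
| Three | colleague | impersonal, then plural | yes | Occupational Health |
| Four | name | first person singular | yes | Chief Executive |

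By its voice, and by elimination, letter two is the intended authority-only letter. As printed it has norms text and no Chief Executive. A matrix of intercept, norms text, Chief Executive sign-off and name greeting then has full rank 4, so aliasing between sign-off and greeting is not complete. But no letter carries authority without norms, so the intended two-by-two does not exist.

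**The intended design.** Remove the norms text from letter two, have the Chief Executive sign it, and leave the greetings alone:

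| Group | Norms (N) | Authority (A) | Named (D) |
|---|---|---|---|
| Standard | 0 | 0 | 0 |
| Social Norms | 1 | 0 | 0 |
| Authority | 0 | 1 | 1 |
| Combined | 1 | 1 | 1 |

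A and D have correlation 1.0. Add a greeting term to the SAP model:

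logit(p) = b0 + bN·N + bA·A + bNA·N·A + d·D

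Because D = A, this equals b0 + bN·N + (bA + d)·A + bNA·N·A. There are five columns and rank 4. Only the sum bA + d can be estimated, whatever the sample size. Dropping the interaction does not help: intercept, N, A and D are four columns of rank 3. On this design 2 × 1,885 = 3,770 staff are named and 3,770 are not.

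**What the trial would register.** The documents give no effect size for a greeting, so this is illustration only. Assume 70% uptake, which the SAP names as the 2017–2018 target and which lies near the 71.6% printed in the letters for QEHB.

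- Detectable difference at 80% power, pooled authority contrast: 2.80 × √(2 × 0.21/3,770) = 3.0 points.
- For the 0/1-coded coefficient, which compares one group with one group: 2.80 × √(2 × 0.21/1,885) = 4.2 points.
- At the protocol's 40% uptake, 0.24 replaces 0.21 and the two become 3.2 and 4.5 points.

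Suppose authority does nothing and the name adds g to a 70% baseline. The Authority odds ratio is then [(0.70 + g)/(0.30 − g)] / (0.70/0.30):

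| g (points) | Reported odds ratio | Power, 1,885 against 1,885 |
|---|---|---|
| 1 | 1.05 | 0.10 |
| 2 | 1.10 | 0.27 |
| 3 | 1.16 | 0.53 |
| 5 | 1.29 | 0.93 |

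**The case against.** The strongest reply is that personal address may have been a declared part of the authority treatment. Appendix 1 says "Within the examples the highlighted areas indicate where these two factors are active", with green for authority, and the colours are not visible in the text available here. If the greeting was green, it was not an overlooked ingredient. That stands as a limit: these documents cannot show that naming was unintended. It does not restore the attribution, because the written definition would then be incomplete and the factor would be a package.

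Second, the protocol body can be read as naming every recipient. If the letters sent did so, there is no alias. This also stands. Appendix 1 is not a secure record of what went out: letter two is visibly wrong, and it is headed as emailed text although Design and methodology says letters also go by internal post.

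Third, the primary question concerns the content of the wording, and randomisation compares whole letters without bias. That is correct, and it limits the point to the name given to the effect. Objective 1 and the primary model do, however, name it Authority.

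Finally, voice and the extra courtesy line track the greeting in the same way. Voice belongs naturally to a letter from a person in authority. The courtesy line does not, and it should be made uniform.

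**Conclusion.** The point holds for the two-by-two that the SAP sets out to analyse. With letter two corrected and the greetings left as printed, being named is completely aliased with Authority, and no model, covariate or sample size can separate the two. The protocol body and Appendix 1 also disagree on who is addressed by name and must be reconciled.

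Three stronger readings are tempting but unsupported:

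- That the trial's comparison is biased. It is not: differences between whole letters are estimated validly, and only attribution to authority alone is lost.
- That 3,770 staff were in fact named and 3,770 were not. No section records the salutations sent, and in the letters as printed the alias with the Chief Executive's sign-off is incomplete.
- That the distortion is about 3 or 4 points. Those figures are detectable differences at an assumed uptake, not estimates of a salutation effect.

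The conclusion assumes that Appendix 1 shows the greetings as used and that letter two was meant as authority only.

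**What to change.** **As designed.** Use the same salutation in all four Appendix 1 letters, and make the courtesy line before the signature uniform. Names are already in the mailing file, so this is a template edit with no new data.

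**As things stand.** SAP section 6 says the letters were sent on 4 October 2018, so the template can no longer change the trial. Confirm the salutations actually used, by email and by internal post, and reconcile them with the protocol's Data/Outcomes and Design and methodology sections.

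- If they differed by group, redefine the factor in SAP Table 1, Objective 1 and the primary analysis as a personally addressed letter from the Chief Executive, and draw no conclusion about authority alone.
- If every letter sent was named, state that in the SAP and keep the Authority label.

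The cost is a check of the letters sent and a few words in the SAP. The model and the data stay the same.

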The decision as to whether the present study requires NHS-REC approval was decided using the Health Research Authority's tools: "Is my study research?"¹ and "Do I need NHS-REC approval?"² The outcomes provided by these tools are described in Table 1.

Table 1.

Is my study reseach?	Yes
Do I need NHS-REC approval?	No but may need other approvals, e.g., HRA and potentially site approvals.

Summary of study. (limit 300 words)

Seasonal vaccination against influenza is recommended for NHS staff.^{3,4} To increase vaccination rates, NHS England put forth a Commissioning for Quality and Innovation goal for the 2018/2019 season of 75%.⁵ University Hospitals Birmingham NHS Foundation Trust (UHB) wants its vaccination rate to surpass this target. Since staff get infected outside of the hospital and from patients staff vaccination does not provide significant 'herd immunity'

To reach past targets, every September UHB already invites staff to take up the vaccination, and regularly reminds staff that have not yet vaccinated to do so. The current protocol describes a randomized controlled trial (RCT) in which staff will be sent a different letter when first invited to receive vaccination, and we will compare the proportion of staff that go on to vaccinate after receiving each type of letter..

To conduct the RCT the research team will design four letter styles. One factor will emphasize an authority figure inviting staff to vaccinate (the Chief Executive, who is also a doctor). The other factor will emphasize a competitive social norm describing vaccination rates in peer hospitals, including Addenbrooke's, Cambridge University Hospitals (which has exemplary rates) see appendix A and across American hospitals (which also have high rates). Letters will be sent to staff in the last week in September by UHB's communications team and they will be disseminated in a randomized fashion.

The UoW's role in this study is to advise the study's design and write-up the project for publication. UHB will approve the reminders, send the reminders, retrieve the data, and analyse the data. No individual-level data will be transferred across organizations. All individual-level data will be managed by authorized UHB employees, e.g., a UHB statistician will randomize staff to receive different reminders and analyze the data, and UHB's communication team to disseminate the reminders.

Questions.

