1. INTRODUCTION

The present Statistical Analysis Plan extends the outcome analyses previously stated in the protocol version 2.0 (ClinicalTrials.gov Identifier: NCT03637036) to clarify how we will handle more analyses and a protocol deviation that occurred during the randomization process.

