2. DATA

Data collection is described in protocol (version 2, page 5). However, deviations from the protocol resulted in modifications to some of the data we will have available for the analyses. Table 1 describes the data contained in the data file.

The first deviation occurred because of the four worksites originally planned to be in the trial, three could not take part. This left one worksite in the trial, i.e. Queen Elizabeth Hospital.

The second deviation affects our plans for sub-group analyses. This occurred because the trust records describe job roles differently than stated in the protocol. So instead of the job roles stated in the protocol, staff were stratified by two Employment-Types and four Job-Types.

The third deviation occurred as 898 (10.6%) of the hospital's 8438 staff randomized were allocated to a fifth, no-letter, control group. The remaining 7,540 staff were randomized to the planned four groups in equal numbers (i.e., 1885 participants to each of four groups). We will analyse data in the four groups per the original protocol and this will be the primary analysis. However, we will also carry out a subsidiary analysis to compare the results of this no-letter control group to the letter groups, as described in the below section titled 'Supplementary Analysis'.

Table 1. Data in the project analysis file

Type	Name	Codes
Intervention	Group Number	0 = Standard, 1 = Social Norms, 2 = Authority 3 = Combined, and 4 = No Letter Control
Demographics	Gender	0 = Female, and 1 = Male
	Type of Employment	0 = Bank, and 1 = Substantive
	Job Type	0 = Healthcare assistants and other support staff, 1 = Medical and dental staff, 2 = Nursing, midwifery and health visiting staff, and 3 = Scientific, therapeutic and technical staff (for the analyses, groups 0 and 3 will be combined)
Primary Outcome	Date of vaccination at Trust	DD-MM-YYYY, or blank if the vaccination was never received
Other outcomes (formally self-reported)	Refusal to take up the Vaccination	0 = No, and 1 = Yes
	Vaccinating at a non-trust location	0 = No, and 1 = Yes

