3. ANALYSIS OBJECTIVES

- Objective 1 is to assess the effects of the two intervention types (Social Norms and Authority) and any interaction effect of these interventions on the on-site vaccination rates by the end of the trial, i.e. 4th of January 2019.
- Objective 2 is to assess the effects of the interventions on subgroups of the study. We are most interested in comparisons across the above stated three job types, though we will also compare the effects across genders. We will not examine the type of employment because the bank sub-group is small, but we will report the proportion of staff taking up the vaccine in this subgroup.
- Objective 3 is to assess cumulative rates of vaccinations across each group by week from the beginning to the end of the study period.

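### No letter printed in Appendix 1 gives the authority message without the norms block, yet the SAP's primary model needs an authority-only group

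*Combined protocol and SAP*

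**What the plan says.** The protocol's Summary of study sets out a two-factor design with four letters: "One factor will emphasize an authority figure inviting staff to vaccinate (the Chief Executive, who is also a doctor", and a second factor giving vaccination rates in peer hospitals. Its Design and methodology section refers the reader to the appendix for the wordings and adds that "Letters will be sent both by e-mail and through the internal post". Appendix 1 prints only the e-mailed versions.

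The SAP relies on the full two-by-two. Section 2, Table 1 codes the groups as "0 = Standard, 1 = Social Norms, 2 = Authority 3 = Combined, and 4 = No Letter Control". Section 3 states that "Objective 1 is to assess the effects of the two intervention types (Social Norms and Authority) and any interaction effect of these interventions". Section 5 makes these three terms the primary model, and section 7 counts staff who were sent an authority letter.

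In Appendix 1, the norms block consists of the national expectation, a five-hospital league table and the closing line "In the United States 92% of hospital staff receive flu vaccination". Letters two, three and four each print it in full, including "However, we want UHB to be amongst the very best performers of similar hospitals, so that we maximise protection for our staff and patients". Letter one does not.

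**The concern.** A two-by-two analysis needs one letter with authority and no norms. None is printed.

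If the letters were sent as printed, the SAP model would still run without warning, because it is coded by group label and not by content. Its Authority and interaction coefficients would then measure something other than their names.

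If a proper authority-only letter was sent, the analysis is sound, but the public protocol misdescribes one of the four primary groups. Either way the documents contradict each other, and the primary result cannot be interpreted until the text behind each label is known.

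**Working it through.** **1. The printed letters side by side (Appendix 1)**

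| Letter | Salutation and voice | Norms block | Signed by |
|---|---|---|---|
| One | generic, impersonal | no | Occupational Health |
| Two | by name, first person | yes | Occupational Health |
| Three | generic, impersonal | yes | Occupational Health |
| Four | by name, first person | yes | Chief Executive |

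**2. Which letter went to which group.** The documents give no firm mapping. Letter two's first-person voice suggests it was meant as the authority letter. The unfinished illustrative coding in the protocol's Data/Outcomes section, "Group Number (e.g., 0=letter version one, 1=letter version two, 2", read with SAP Table 1, would instead make letter two Social Norms and letter three Authority. That reading is weaker, since letter three has no authority wording. Under both, the letter labelled Authority carries the norms block.

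**3. The plan's own sample size.** It states 750 per group for an interaction with uptake of 40, 40, 40 and 50%, alpha 0.05 and power 0.80.
- Risk-difference scale: n = (1.960 + 0.842)² × (3 × 0.24 + 0.25) / 0.10² = 7.849 × 0.97 / 0.01 = 762.
- Log-odds scale: n = 7.849 × 16.5 / (ln 1.5)² = 788.

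The stated figure is reproduced to within 3% on the first scale. It presumes four distinct factorial cells.

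**4. Identification.** On the log-odds scale let b be the base, g the norms effect, s the first-person style with named salutation, and c the Chief Executive's signature. Then L1 = b, L2 = b + g + s, L3 = b + g, L4 = b + g + s + c.

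- If letter two is Authority: Authority coefficient = L2 − L1 = g + s; Norms coefficient = L3 − L1 = g.
- If letter three is Authority: Authority coefficient = L3 − L1 = g; Norms coefficient = L2 − L1 = g + s.
- In both cases: interaction = L4 − L3 − L2 + L1 = c − g.

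Coded by content, with norms = (0,1,1,1) and authority = (0,1,0,1) or (0,0,0,1), the matrix of intercept, norms, authority and product has rank 3. The intended design has rank 4.

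**5. Size, if the letters went out as printed.** Inputs: 1885 per group (SAP section 2), and base uptake of 40% (protocol sample-size text) or 70% (near the 71.6% printed for QEHB). The norms effect is an assumption, because the documents give none. With s = c = 0 both mappings give the same figures. Two-sided 5% Wald tests; variance = sum of 1/(n p(1 − p)) over the groups in the contrast.

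Example, 40% base and 5 points: g = ln(0.45/0.55) − ln(0.40/0.60) = 0.205, OR 1.23. The SE for Authority is 0.066, so z = 3.10 and the rejection probability is 87%. The SE for the interaction is 0.093, so z = 2.20 and the probability is 60%.

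| Assumed norms effect | False Authority (40% / 70% base) | False interaction | At least one |
|---|---|---|---|
| 0 points | 5% / 5% | 5% / 5% | 8% / 8% |
| 2 points | 24% / 27% | 14% / 16% | 28% / 32% |
| 3 points | 46% / 53% | 26% / 30% | 50% / 57% |
| 5 points | 87% / 93% | 60% / 67% | 89% / 94% |

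The last column comes from simulation with 200,000 runs per case. The spurious ORs at 2 points are 1.09 / 1.10 (Authority) and 0.92 / 0.91 (interaction). At 5 points they are 1.23 / 1.29 and 0.81 / 0.78.

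**6. Sensitivity.** Style and signature effects are set in points at the base rate and carried over as log-odds.
- Norms effect of 2 points, style effect of −1 to +1 point: the Authority coefficient is significant in 9–47% / 11–52% of trials if letter two has that label, and is unchanged if letter three has it.
- Signature effect of 2 points: it cancels the false interaction at a 2-point norms effect (5%) and cuts it to 26% / 31% at 5 points. If the 2 points are added directly to letter four's uptake, the latter pair becomes 27% / 27%.

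**7. What stays estimable.** Three against one gives norms alone. Four against three gives the authority package in the presence of norms. Four against two gives the signature, given norms and first-person style. Each has 80% power for about 4.5 / 4.1 points from a 40% / 70% comparator, or 5.2 / 4.7 with Bonferroni over three.

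**The case against.** The best defence is that the fault lies in the appendix alone. Letter two departs from the described design twice, in its norms block and in its departmental signature under a first-person invitation, which looks like a pasted draft. The SAP was written after the letters went out on 4 October 2018, partly to "clarify how we will handle more analyses and a protocol deviation that occurred during the randomization process". It lists three deviations, none about letter content, and consistently names an authority group.

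This makes an appendix error plausible but does not settle it. Sending the letters as printed would have followed Appendix 1, so nobody need have seen a deviation to report. Sending a true authority-only letter would have departed from the printed text, yet that is not reported either. SAP section 9 also records that hospital staff created a fifth group without the University team's knowledge, so delivery cannot be assumed to match intention.

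The green and yellow highlighting is not visible in the text reviewed. It could show whether the salutation and first-person voice belong to the authority factor. It cannot explain a full league table in letter two.

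It is also fair to say that the rejection rates rest on an assumed norms effect and an unconfirmed event. The non-identification argument needs neither an assumed effect size nor a sample size; it needs only that the printed text was sent.

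**Conclusion.** The concern holds. As printed, Appendix 1 contradicts the SAP's Authority group and interaction, and this must be resolved before the primary analysis can be interpreted. The printed inconsistency is certain; the damage to the analysis is conditional on the printed letters having been sent.

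On that condition, authority without norms and the true interaction are not identified. A norms effect of 2 to 5 points, with no style or signature effect, would produce at least one misleading significant term in roughly 28% to 94% of trials, depending on its size and the base uptake. If a genuine authority-only letter was sent, the planned analysis stands and only the protocol record is wrong.

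**What to change.** 1. Before the data-lock on 4 January 2019, obtain and document the text sent to each group, by e-mail and by internal post. Add a line to SAP section 2 stating which letter each Table 1 group received. Do not change Appendix 1 until this is done.
2. If a true authority-only letter was sent, correct Appendix 1 to show it and keep the analysis.
3. If the letters went out as printed, leave Appendix 1 as the record and add an entry to SAP section 2 saying that the letters did not form the intended two-by-two. Analyse the four letters as distinct groups with pre-specified contrasts: three against one, four against three, four against two. Name one as primary or state a multiplicity rule. Drop claims about authority alone and about the interaction.
4. If the sent text confirms that the salutation differs between letters, say that the authority effect includes it.

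The cost is one check of the sent material and one mapping line, then either one corrected letter or one SAP entry with new contrast wording. No extra participants or data are needed. Settling it before outcome data are received keeps the choice of contrasts independent of the results.
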